Although a majority of treated patients show a benefit, up to 40% derive no improvement from CRT. In the MIRACLE study, 34% of patients did not demonstrate an improvement in a HF clinical composite score (CCS) that combined all-cause mortality, HF related hospitalization, NYHA class and patient global assessment into an outcome measure⁹. A summary of non-responder rate from various clinical studies has been performed by Birnie and Tang¹⁰. Those rates of non-response to cardiac resynchronization therapy are often quoted as 20-30% in the listed studies, but the authors suggest that the true non-responder rate may be as high as 40-50%. This inconsistent CRT effectiveness may be due to incomplete resynchronization and the presence of Intraventricular dyssynchrony.

The cause for failed response to CRT is not completely understood; there is a general consensus, supported by growing evidence, that suboptimal LV lead placement accounts for a large percentage of patients who do not respond to CRT.

Some studies have shown that lateral and postero-lateral lead placements have more favorable results than other locations, but the link between lead location and clinical benefit is not yet well understood¹¹⁻¹⁶. Several methods have been used in attempts to optimize lead placement including using intracardiac electrograms to locate the site of most delayed activation, measuring acute hemodynamic response based on lead location; using scar burden and location to predict response; and using electrical mapping to optimize epicardial Left Ventricle (LV) lead placement¹⁷⁻²². However, unfavorable coronary venous anatomy with narrow and tortuous tributaries, phrenic nerve stimulation, high capture thresholds, or pacing lead instability

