[figure not shown]

[figure not shown]

[figure not shown]
Version 1.1, September 25, 2009

[figure not shown]

[figure not shown]

Part 2 - Packer's Clinical Composite Score (CCS)

The Packer's Clinical Composite Score (CCS) will be assessed at 6 months and 12 months post implant.

The CCS includes 4 components: NYHA class, Patient Global Assessment (PGA), HF events, and cardiovascular death²⁷.

The NYHA Class evaluation and PGA will be determined by an Investigator interviewing subjects about their symptoms. Specifically, the PGA will be a single interview question that asks the subject to categorize how they feel compared to their previous visits as either:

- Markedly better
- Better
- No change
- Worse
- Markedly worse

At the 6 Months Follow Up visit, a PGA will be conducted to evaluate how the subject feels compared to the baseline visit before having the CRT system implanted.

At the 12 Months Follow Up visit, two different PGAs will be conducted:

- The first one will evaluate how the subject feels compared to the baseline visit before having the CRT system implanted and
- The second one will evaluate how the subject feels compared to the 6-month visit.

In this trial a **HF event** is defined as any one of the following when the subject has symptoms and/or signs consistent with congestive heart failure:

- Hospitalization or Emergency Department visit for HF \geq 24 hours
- Hospitalization or Emergency Department visit for HF $<$ 24 hours requiring administration of IV inotropes or diuretics

Finally, **cardiovascular death** is defined as sudden unexpected death; heart failure death; myocardial infarction related; or 'other' such as pulmonary embolism, peripheral thromboembolism, stroke, deaths due to vascular procedure, or other major cardiovascular event.

Using the CCS decision algorithm described below, subjects are categorized as Improved, Worsened or Unchanged based on the following rules:

IMPROVED – subjects that demonstrate:

- At least a one-class improvement in NYHA Class OR improvement by PGA ("Better" or "Markedly better")
AND
- No HF events as described above
AND
- No Cardiovascular death

[figure not shown]
WORSENERD – subjects that demonstrate:

[figure not shown]
- Worsening in NYHA Class OR worsening by PGA ("Worse" or "Markedly worse")

[figure not shown]
- OR
- Presence of HF events as described above
- OR
- Cardiovascular death

[figure not shown]
UNCHANGED – subjects that are neither “Improved” nor “Worsened”.

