5.2 Secondary Endpoints**5.2.1 Percent reduction (%) in LVESV from baseline to 6 months**

Percent reduction (%) in LVESV from baseline to 6 months will be summarized as sample size, mean, standard deviations, median and range. Subjects with missing LVESV at either Baseline or 6 months visit will be excluded from this analysis.

5.2.2 Packer’s Clinical Composite Score evaluation between baseline and 12 Months visit and between 6 months and 12 months visits.

Using the Packer’s clinical composite score (CCS), subjects are categorized as Improved, Worsened or Unchanged based on the following rules:

- “Worsened” – subjects that demonstrate:
 - Worsening in NYHA Class at last observation carried forward (LOCF) OR worsening by PGA (“worse” or “markedly worse”) at LOCF
OR
 - Presence of HF events as described in CIP
OR
 - Cardiac death
- “Improved” – subjects that demonstrate:

Study Document No: [REDACTED]

[figure not shown]
Study Name: MORE CRT MPP

Statistical Analysis Plan

- At least a one-class improvement in NYHA Class at LOCF OR improvement by PGA (“better” or “markedly better”) at LOCF
AND
- No HF events as described in CIP
AND
- No cardiac death

- “Unchanged” – subjects who have non-missing NYHA at LOCF or non-missing PGA at LOCF and are neither “Improved” nor “Worsened”.

If both NYHA and PGA are missing based on LOCF and doesn't have HF event and cardiac death, they will be excluded from the analysis.

Statistical Analysis Plan

Statistical Analysis Plan**5.2.3 Reverse LV remodeling, measured as % changes in LVESV, [REDACTED] and LVEF**

- [REDACTED]
- [REDACTED]

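### On the Clinical Composite Score, a death outside the cardiac (SAP) or cardiovascular (protocol) category does not itself count as Worsened, and carry-forward can score the dead subject Improved

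*Combined protocol and SAP*

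**What the plan says.** The Clinical Composite Score (CCS) is a listed secondary endpoint, evaluated from baseline to 12 months and from 6 to 12 months (protocol 3.3.2, SAP 4.2). Protocol 7.3 plans between-group comparisons of the categorical secondary endpoints.

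SAP 5.2.2 gives three routes to Worsened: "Worsening in NYHA Class at last observation carried forward (LOCF) OR worsening by PGA"; "Presence of HF events as described in CIP"; or cardiac death. Improved requires "At least a one-class improvement in NYHA Class at LOCF OR improvement by PGA", no heart-failure (HF) event, and "No cardiac death". A subject leaves the analysis only under the rule that begins "If both NYHA and PGA are missing based on LOCF", and then only without an HF event or cardiac death.

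Protocol Appendix E Part 2 uses a different fatal component: "The CCS includes 4 components: NYHA class, Patient Global Assessment (PGA), HF events, and cardiovascular death". Its definition of cardiovascular death extends beyond the heart to causes "such as pulmonary embolism, peripheral thromboembolism, stroke, deaths due to vascular procedure, or other major cardiovascular event".

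On timing, protocol Table 2 schedules NYHA class at baseline, 6 and 12 months, and the Patient Global Assessment (PGA) at 6 and 12 months only. Randomisation takes place at the 6-month visit, and MPP stays off until then.

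**The concern.** A death that is not cardiac under the SAP, or not cardiovascular under the protocol, appears in neither the Worsened nor the Improved rule. The subject is then scored on symptoms recorded while alive. For a death between the 6- and 12-month visits, the last scheduled NYHA and PGA come from the 6-month visit, before the randomised programming had any time to act. If that visit was better than baseline, the subject meets every written condition for Improved from baseline to 12 months.

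A score meant to show the effect of MPP on clinical status would then contain subjects who died and were counted as successes on pre-randomisation data. The recorded cause of death would also decide the category, and the readable text describes neither blinding nor an independent committee to classify deaths.

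**Working it through.** The documents state no CCS rate, power or sample size, so there is no planned figure to reproduce. The check is of the classification rule.

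**1. Every input pattern for a subject who died.** NYHA at the last observation is better, same, worse or missing; PGA likewise; an HF event is present or absent. That gives 4 × 4 × 2 = 32 patterns. For a death that the rule does not name:

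- HF event present: all 16 patterns are Worsened.
- HF event absent, NYHA or PGA worse: 4 + 4 − 1 = 7. In 2 of these the other item is better, so the subject meets both definitions as written. The other 5 are Worsened only.
- HF event absent, nothing worse, at least one item better: (3 × 3) − (2 × 2) = 5, Improved.
- HF event absent, nothing worse or better: 2 × 2 = 4, of which 3 are Unchanged and 1 (both missing) is excluded.

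The total Worsened only is 16 + 5 = 21, and 21 + 2 + 5 + 3 + 1 = 32. These are counts of patterns, not probabilities.

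**2. The same 32 patterns by cause of death.**

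| Cause of death | SAP fatal component (cardiac) | Protocol fatal component (cardiovascular) | Any death |
|---|---|---|---|
| Cardiac | 32 Worsened | 32 Worsened | 32 Worsened |
| Cardiovascular, not cardiac (e.g. stroke) | 21 Worsened, 2 both, 5 Improved, 3 Unchanged, 1 excluded | 32 Worsened | 32 Worsened |
| Non-cardiovascular | 21 / 2 / 5 / 3 / 1, as above | 21 / 2 / 5 / 3 / 1 | 32 Worsened |

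The protocol column applies the SAP's carry-forward and exclusion rule, so that only the fatal component differs. The protocol has neither rule, and its section 7.6 rules out imputation. On its text alone, a subject with no 12-month symptom data, no HF event and a non-cardiovascular death falls into Unchanged by default.

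The middle row shows the conflict between the documents. The bottom row shows that agreeing on cardiovascular would not close the gap.

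**3. The 6-to-12-month score.** Carrying the 6-month NYHA forward gives no change, so the subject tends to be Unchanged. The 6-month PGA is asked against baseline; the PGA against 6 months exists only at the 12-month visit. Improved could arise here only if the 6-month PGA were carried into this comparison, which the readable SAP does not settle.

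**4. Size, on assumed rates.** Let d be the share of an arm dying of an unnamed cause between 6 and 12 months, and q the share of those who meet Improved. The share moved from Improved to Worsened by an any-death rule is d × q.

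- Low: 0.5% × 30% = 0.15 percentage points.
- Middle: 1% × 50% = 0.50 percentage points.
- High: 3% × 70% = 2.1 percentage points.

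Per 1,000 randomised subjects this is 1.5 to 21. Neither d nor q comes from the documents. A trial-wide count would need the number randomised, which cannot be read, and the protocol gives two totals for Qualified Subjects (5638 in section 3.5, 5914 in section 3.10.2).

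**The case against.** Five points can be made for the plan.

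- **The rule is the same in both arms.** The carried value normally predates randomisation, so it should differ between arms only by chance. This stands: a reader might infer a bias towards MPP ON, and the documents show no mechanism for one. Equal application does not make Improved a meaningful category for a subject who has died.
- **Cause-specific handling of death is this trial's convention.** For the primary endpoint, cardiac deaths are non-responders and subjects who fail to complete follow-up for other reasons are excluded (protocol 3.4 and 7.4). That is a fair defence of a cause-specific component. But SAP 5.2.2 does not exclude these subjects; it scores them on carried symptoms.
- **The deaths are not hidden.** SAP 6.2 reports all-cause and cardiovascular mortality by arm from randomisation. This is true, and it limits the harm to interpretation of the CCS.
- **The text is incomplete.** The CCS algorithm figure is not shown. The SAP contents list puts 5.2.2 on page 12 and 5.2.3 on page 15, and part of that span is not legible. A rule for other deaths could sit in either place. This stands as a limit on the point, although the category and exclusion rules that can be read contain none.
- **The protocol's background is not a definition.** Section 2 describes a score that "combined all-cause mortality, HF related hospitalization, NYHA class and patient global assessment into an outcome measure". A reader might infer that the plan contradicts its own definition. It does not: that sentence describes an earlier CRT study, and the protocol consistently gives this trial's score a cardiovascular-death component.

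**Conclusion.** The point holds for the readable rules. A non-cardiac death (SAP) or non-cardiovascular death (protocol) does not itself count as Worsened. Absent an HF event or symptom worsening at the last observation, carry-forward can score that subject Improved from baseline to 12 months. The SAP and protocol also disagree on which deaths count.

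Two stronger readings should be resisted. A reader might infer that such a subject can never be Worsened; an HF event, or NYHA or PGA worsening at the last observation, still gives that result whatever the cause of death. A reader might also infer that the carried value always predates randomisation; an unscheduled visit can record a later NYHA class (protocol 4.2.7), so this is the usual case only.

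The number affected is probably small: 0.15 to 2.1 percentage points of an arm, wholly on assumed rates. This is one secondary endpoint, and the primary endpoint is untouched. The point is worth correcting because a stated rule gives a wrong answer and the correction is cheap, not because it threatens the trial's main conclusion.

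**What to change.** In SAP 5.2.2 and protocol Appendix E Part 2, state that death from any cause after randomisation is Worsened for both scores, and that this is applied before any NYHA or PGA rule. Keep a version limited to cardiovascular death as supportive, with one definition of that term used in both documents. If the illegible part of SAP 5.2.2 or the algorithm figure already contains a rule for other deaths, bring the written category rules into line with it. State also whether the 6-month PGA may be carried into the 6-to-12-month score, and reconcile the SAP's carry-forward with the no-imputation statement in protocol 7.6.

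The cost is a few words in two places. No new data are needed: every death is already recorded on the Death form (protocol 5.4.1), and all-cause mortality is already analysed (SAP 6.2). The main rule would no longer depend on the recorded cause of death. Against this, deaths unrelated to pacing add slight noise in both arms, and the Phase I score would have to be re-run if it has already been analysed.

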5.2.4 NYHA Class changes

- [REDACTED]
- [REDACTED]

5.2.5 6-minute walk test changes

- [REDACTED]

Statistical Analysis Plan

- [REDACTED]

5.2.6 Quality of Life (MLWHF and EQ-5D) changes

- [REDACTED]

- [REDACTED]

5.3 Overall Sample Size

A total number of up to 6896 subjects will be enrolled (see section 5.1.1.4).

5.4 Trial Success

[REDACTED]

5.5 Multiplicity Adjustment

No multiplicity adjustment is planned in this study.

Statistical Analysis Plan**6.0 ADDITIONAL DATA****6.1 Baseline and Demographic Characteristics**

Descriptive statistics of continuous variables will be presented by treatment group and include sample size, mean median, standard deviation, minimum and maximum. For categorical variables, the number and percentage of subjects in each category will be presented by treatment group. Baseline characteristics will be tabulated and compared between the two treatment groups. Categorical variables will be tested using Fisher's exact test and continuous variables will be tested using two sample t-test.

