6.4 Treatments in case of premature study termination

In case the study will be prematurely terminated, subjects will return to the Center's routine follow-up schedule. The device programming will be left at physician's discretion and no study-related activities will be performed.

7 Statistical considerations

The following section describes the statistical methods for the clinical investigation. Additional details on statistical analyses, including study cohorts, subgroup analyses and analysis of secondary endpoints are maintained in a separate Statistical Analysis Plan (SAP).

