7.2.1.2 Data Analysis of Phase II Subjects

The analysis will be performed when all randomized non-responder subjects (confirmed by the Echo Core Lab) from the Phase II study have either completed or crossed the 12 month visit window or discontinued before the 12 month visit.

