5.1.1 Analysis Methods

The hypothesis will be tested at the one-sided 2.5% significance level. The null hypothesis will be rejected if the 97.5% lower confidence bound (LCB) for the difference between the proportion of subjects who are responders in the treatment group (MPP ON) and the proportion of subjects who are responders in the control group (MPP OFF), $(P_{ON}-P_{OFF})$, is greater than 0. The 97.5% LCB will be calculated using the Wald asymptotic confidence limits for difference of binomial proportions. [REDACTED]

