5.1.2 Analysis Population

The primary endpoint analysis will be carried out on three subject cohorts:

- The **first subject cohort** (Cohort #1) [REDACTED]

- The **second subject cohort** (Cohort #2) [REDACTED]

- The **third subject cohort** (Cohort #3) [REDACTED]

Study Document No: [REDACTED]

Study Name: MORE CRT MPP

Statistical Analysis Plan

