5.1.5 Timing of Analysis**Data Analysis of Phase I Subjects**

The analysis will be performed when all randomized non-responder subjects (confirmed by the Echo Core Lab) from Phase I study have either completed or crossed the 12-month visit window or discontinued before the 12-month visit. This analysis will be carried out on Cohort #1.

Data Analysis of Phase II Subjects

One interim analysis and a final analysis will be conducted.

- Interim Analysis

[REDACTED]

[REDACTED]

- The final analysis will be performed when all randomized non-responder Phase II subjects have either completed or crossed the 12-month visit window or discontinued before the 12-month visit.

Statistical Analysis Plan

- [REDACTED]
- [REDACTED]

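### Does the SAP's statement that nothing is adjusted for multiplicity conflict with a Phase II interim analysis that the protocol does not mention?

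*Combined protocol and SAP*

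**What the plan says.** SAP 5.1.1 tests the primary hypothesis at one-sided 2.5%: "The null hypothesis will be rejected if the 97.5% lower confidence bound (LCB") for the difference in responder proportions, MPP ON minus MPP OFF, lies above 0. A redacted block follows that rule.

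SAP 5.1.2 says "The primary endpoint analysis will be carried out on three subject cohorts"; the cohort definitions are redacted.

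SAP 5.1.5 says of Phase II: "One interim analysis and a final analysis will be conducted". What stands under the interim bullet is redacted. The final analysis is visible: "The final analysis will be performed when all randomized non-responder Phase II subjects have either completed or crossed the 12-month visit window", or discontinued earlier. SAP 5.1.6 plans a check of whether Cohorts #2 and #3 can be pooled, at both the interim and the final analysis; its rules are redacted.

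SAP 5.4 (Trial Success) is wholly redacted. SAP 5.5 is a single visible sentence: "No multiplicity adjustment is planned in this study".

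Protocol 7.2.1.2 gives one Phase II trigger: "The analysis will be performed when all randomized non-responder subjects (confirmed by the Echo Core Lab) from the Phase II study have either completed", crossed the 12-month window or discontinued. The opening of protocol section 7 passes further matters on: "Additional details on statistical analyses, including study cohorts, subgroup analyses and analysis of secondary endpoints are maintained in a separate Statistical Analysis Plan (SAP").

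**The concern.** Protocol 7.2.1 and SAP 5.1.5 share a title and agree on when Phase I is analysed. For Phase II the SAP has one more analysis than the protocol, so someone reading only the protocol would not expect an interim. The protocol's list of matters left to the SAP does not name interim analyses.

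The disclaimer in SAP 5.5 is unqualified. It does not say whether it covers the two looks, the three cohorts or only the endpoints. If the interim could end Phase II with a claim of success at the same 97.5% bound that serves the final analysis, the chance of a false claim in Phase II would exceed 2.5%. If instead a spending boundary sits in the redacted part of 5.1.5, a literal reading of 5.5 would contradict it. In either case the 97.5% bound in 5.1.1 might not be the right final bound.

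**Working it through.** **The plan's own figure.** A 97.5% lower bound corresponds to one-sided alpha = 1 − 0.975 = 0.025, critical value 1.960. This agrees with the level stated in SAP 5.1.1. Response rates, power, randomized numbers and interim timing are not visible, so nothing further can be reproduced.

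**What would be at stake.** Let Z1 and Z2 be the interim and final test statistics under the null, approximately bivariate normal with correlation √t, where t is the fraction of information at the interim. The documents give no t; the values below are assumed.

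- Interim can declare success at the unadjusted level: error = 1 − P(Z1 < 1.960, Z2 < 1.960).
- Interim can only stop for futility, here taken as stopping when the interim difference is below 0: error = P(Z1 ≥ 0, Z2 > 1.960).

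| t (assumed) | √t | P(both below 1.960) | Error, success possible at both looks | Error, futility only |
|---|---|---|---|---|
| 0.25 | 0.500 | 0.9546 | 4.54% | 2.27% |
| 0.50 | 0.707 | 0.9584 | 4.16% | 2.47% |
| 0.75 | 0.866 | 0.9633 | 3.67% | 2.50% |
| 0.90 | 0.949 | 0.9676 | 3.24% | 2.50% |

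Whether the level is exceeded therefore depends on what the interim is allowed to do, and that rule is redacted. The table cannot say which column applies.

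**The possible contents of the redacted text.**

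1. *A spending boundary.* The error is controlled. SAP 5.5 conflicts with it only if multiplicity there includes repeated looks. SAP 5.0 opens the section by counting one primary and 6 secondary endpoints, and 5.5 comes at its end, after the secondary endpoints and trial success. Reading it as a statement about endpoints is at least as natural.
2. *Success possible at an unadjusted 2.5%.* This would be an error, of the size in the fourth column. No visible sentence says the interim works this way.
3. *Futility or a similar non-claiming purpose.* No adjustment is needed for the interim and 5.5 is correct.
4. *A data-driven change, for instance to the analysis set or the sample size.* An interim that makes no efficacy claim can still raise the error if it steers the final analysis. The only visible use of the interim, the pooling check in SAP 5.1.6, could be of this kind, but its rules are redacted too.

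**Protocol against SAP.** The protocol's Phase II trigger and the SAP's final-analysis trigger rest on the same three outcomes: completed, crossed the 12-month window, or discontinued before the visit. The one visible difference is that the protocol repeats the core-lab confirmation and the SAP sentence does not. The protocol sentence thus fits the final analysis, with the SAP adding an earlier look. The absence of an interim from the visible protocol is also weak evidence, because 7.1.2 (Phase II sample size) and the design part of the synopsis each contain redacted blocks.

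**The case for a change.** The strongest case for a change is that the number of Phase II analyses differs on visible text. Redaction hides how the interim works, not that it exists. The protocol sets analysis timing itself in 7.2.1, and a look at accumulating primary-endpoint data is more than a detail. SAP 5.5 shows no exception or cross-reference. A few sentences would settle the matter, and a clarification written after Phase II data had been seen could look data-driven.

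Part of this stands. A protocol reader is not told in the visible text that an interim takes place, and a sentence in 7.2.1.2 with a cross-reference in SAP 5.5 would make the documents easier to read. That is an editorial gain. The protocol's list of matters left to the SAP is introduced as examples, so an interim specified only in the SAP is not excluded.

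The multiplicity part does not stand. It needs either a literal reading of 5.5 set against a boundary nobody can see, or an unadjusted efficacy stop that no visible text describes. Text blacked out of the public copy cannot be counted as missing from the plan. A reader of the complete SAP has the remainder of 5.1.1, the interim rule and the success rule, and may have no doubt about the final bound. Supplying replacement wording from outside also carries a risk: a sentence saying that no adjustment is needed because the interim cannot claim efficacy would be a wrong justification if the interim pooling check steers the final analysis.

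**Conclusion.** The visible sentences are as described, but they establish no statistical fault. The protocol and SAP can be read together, with the protocol giving the final Phase II analysis and the SAP adding an interim before it. SAP 5.5 is compatible with an interim that cannot claim success, and with a spending boundary if it speaks of endpoints. The 3.2% to 4.5% range applies only under an assumed efficacy stop at an unadjusted 2.5% and assumed information fractions from 0.90 down to 0.25. It is not an estimate for this trial, and no claim of an inflated error or a wrong final bound rests on it.

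A cross-reference would only write down what the redacted sections may already specify. It would alter no test, bound, sample size or conclusion visible in the documents, so the plan needs no change on this point. This judgement is limited to the public text: it does not certify the redacted interim rule, and a visible rule allowing an unadjusted claim of success at the interim would reverse it.
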